17.6 Secondary Efficacy Analysis

Secondary analysis of categorical data will be performed using Fisher's exact test for paired samples.

18. Safety Analysis

Safety will be assessed by evaluation of adverse events and clinical laboratory results and derived as data sets and frequency methods.

An independent Data and Safety Monitoring Board (DSMB) will follow the DSMB charter for this study. The DSMB Charter is commensurate with the level of risk of the study to its participants, complexity of the protocol, and ensure compliance with the principles and process of informed consent as well as privacy related regulations (e.g., HIPAA); and to monitor safety by recording (un-)expected adverse events (AEs) and their severity and attribution. The DSMB Charter includes a plan for periodic reviews of primary results and summary data as well as assessment of completeness and quality of collected data. All unexpected and/or serious adverse events as well as premature study withdrawals will be brought to the attention of the DSMB as early as possible in order for the DSMB to make judgments about participant safety, study modifications, and/or continuation. Not beyond the commencement of the proposed subsequent dose escalated cohorts, the DSMB will review study status to determine study progression. These will be based upon discussions between the research team and DSMB, and the decision of the board; no set stopping or escalating rules will be employed. The DSMB membership list is as follows:

[name], PhD - Chair and Research Monitor
MGH, Dana Farber/Harvard Cancer Center
Division of Hematology Oncology
[name]
[name]
Phone: [[name]]([contact])
Fax: [[name]]([contact])
Email: [contact]

[name], - Member
University of Minnesota
Department of Pediatrics
[name]
[name]
[name]
Phone: [[name]]([contact])
Fax: [[name]]([contact])
Email: [contact]

[name], Member (Statistician)
Director, Cooperative Studies Program Coordinating Center
Hines VA Hospital, CSPCC (151K)
[name],
[name]
Phone: [[contact]]([contact])
Fax: [[contact]]([contact])
[contact]

19. Research Monitor

The Research Monitor, [name] [name], is responsible to oversee the safety of the research and report observations/findings to the Human Studies Committee (HSC) or a designated institutional official. The Research Monitor will review all unanticipated problems involving risks to subjects or others associated with the protocol and provide an independent report of the event to the HSC. The Research Monitor may discuss the research protocol with the investigators; shall have authority to stop a research protocol in progress, remove individual human subjects from a research protocol, and take whatever steps are necessary to protect the safety and well-being of human subjects until the HSC can assess the monitor's report; and shall have the responsibility to promptly report their observations and findings to the HSC or other designated official and the HRPO.

20. Adverse Events

Adverse events will be coded to system organ class and preferred term using MedDRA. All adverse events occurring after the initiation of the study treatment (treatment emergent adverse events) will be reported, including events present at baseline that worsened during the study.

Adverse events will be summarized by treatment group to provide visual comparison among the treatment groups with respect to incidence of adverse events (the number of subjects reporting at least one episode of a specific adverse event), incidence of adverse events by severity within body system, incidence of adverse events by attribution within body system, and incidence of adverse events causing withdrawal and incidence of serious adverse events. Regarding severity and attribution summaries, the most extreme outcome (highest severity and closest to study drug related) will be used for those subjects who experience the same adverse event on more than one occasion.

Written narratives will be provided for all serious, unexpected or other significant adverse events that are judged to be of special interest because of their clinical importance.

21. Clinical Laboratory

Clinical laboratory results will be summarized with descriptive statistics at baseline each study timepoint and with shifts from baseline.

22. Data Handling and Recordkeeping

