- 3) Place a human fibroblast growth factor-2 (FGF-2) soaked pledget of bioabsorbable gelatin sponge larger than the tympanic membrane so the tympanic membrane is completely covered.
- 4) Secure the pledget in place with several drops of fibrin glue.
- 5) After the effects of the topical anesthetic have worn off, if any, the patient is released with the following instructions:
 - a) Avoid violently sniffling or blowing the nose
 - b) Sneeze and cough naturally through the mouth without occluding the mouth with the hand.
 - c) Use cotton balls covered with petroleum jelly on the outer surface when washing the hair and bathing. This is needed to help keep water out of the ear.
 - d) Avoid using a hearing aid in the treated ear.
 - e) Avoid flying, using elevators in tall buildings, and other situations involving substantial changes in air pressure.
 - f) Avoid swimming.

DISCONTINUATION FROM TREATMENT:

Reasons for permanent discontinuation include the following:

If the first treatment does not result in complete closure, subsequent treatments will not be administered if any ear complications occur in the treated ear, including but not limited to infection, moderate to severe pain, moderate to severe irritation, or clinically significant sensorineural hearing loss. All subjects will complete all safety follow up visits.

PRIMARY ENDPOINT:

The tympanic membrane and surrounding structures will be examined every 21-days (+7 days) for up to three visits. Adverse events will be recorded at all visits. Routine laboratory tests will be performed at the screening visit and at the final study visit. Vital signs will be assessed at each study visit and changes in clinical examination findings will be noted.

SECONDARY ENDPOINTS:

- Tympanic membrane perforation closure determined by otoscopic exam and photographic documentation
- Pure-tone and speech discrimination scores as measured by pre- and post-treatment audiograms
- Mobility of the tympanic membrane as measured by tympanometry
- Salvage rate of FGF-2 in patients who fail placebo

STATISTICAL ANALYSIS:

The target enrollment of 75 subjects will provide sufficient power while also accounting for potential retention issues. The primary endpoint is to confirm the efficacy of

FGF-2 in subject with TMR by testing the hypothesis that the rate of subject with complete closure of the TMR will be superior to that placebo.

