4.2 Secondary Objectives

- Determine the time to closure of tympanic membrane perforation for FGF-2 group and placebo group.
- Measure changes in pure-tone and speech discrimination scores in all study subjects.

- Determine mobility of tympanic membrane as measured by tympanometry in all study subjects.
- Observe salvage rate of FGF-2 treatment in subjects who failed placebo treatment.

5. Investigational Plan

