5.1 Overall Study Design and Plan Description

This study is a double blinded, placebo controlled phase II study evaluating the efficacy of FGF-2 for the treatment of chronic non-healing tympanic membrane perforations (TMP). The documentation of TM closure will be the main efficacy outcome measure. Pretreatment photographs will document the area of the TM perforation and allow measurement of surface areas of the TMP for comparison of pre- and post-treatment. The study will be divided into two phases, the Randomized Treatment phase (part A), and the Unblinded Crossover phase (part B). In part A of the study, subjects will be randomized 3:1 to receive FGF-2 or placebo treatment up to 3 treatments. Subjects that fail three study treatments will move on to part B of the study. Subjects who received placebo in part A and failed three placebo treatments will crossover to receive unblinded FGF-2 for up to 3 treatments. Subjects who received FGF-2 in part A and failed three experimental treatments will not have additional FGF-2 treatment, and will move on to study follow up.

The primary outcome for the study will be to determine the TMP closure efficacy of FGF-2 and placebo, with up to 3 treatments each. The OBD was determined to be 100 μ g of FGF-2 per 1 mL with an estimated dose of about 20 μ g in 0.2ml in prior studies by [name] (Kanemaru et al., 2011).

Secondary outcomes for the study include: (1) Determination of the time to closure of tympanic membrane perforation, (2) Measurement of changes in pure-tone and speech discrimination scores, (3) Determination mobility of tympanic membrane as measured by tympanometry, and (4) Observation of salvage rate of FGF-2 treatment in subjects who failed placebo treatment.

If both ears are affected by chronic perforation, only one ear will be initially enrolled in the study and receive treatment. The ear with the more significant symptoms will be the one enrolled in the study (i.e., greater conductive hearing loss). The non-study ear will not be enrolled or undergo additional treatments during the study period.

- 1) In an outpatient examination, the subject will be confirmed to have a tympanic membrane perforation by microscopic otoscopy and that no active infection and/or inflammation is present. Then a cotton ball soaked in 4% lidocaine jelly will be inserted with micro alligator forceps directly to the surface of the tympanic membrane under microscopic visualization.

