13.2 Efficacy Measurements

- Dose limiting toxicity/Optimal Biologic Dose is as defined in section 7.1
- TM closure is defined as complete closure of the tympanic membrane durable at both 21-days (± 7 days) and the test-of-cure Visit 5.
- TM Photographs will be obtained at every visit. A series containing pre- and post-treatment images will be digitally secured with Leica M320 high definition digital camera mounted with the Leica Microscope or with a 2.7 mm rigid Storz endoscope.
- Audiometric studies including pure tones (0.25, 0.5, 1, 2, 4, and 8 kHz) and speech discrimination scores will be recorded pretreatment and post treatment. A change of >10 dB across two frequencies or a change in speech discrimination of $> 20\%$ will be considered clinically significant on an NU-50 word list.
- Mobility of the tympanic membrane as measured by a Grayson Stadler GSI 37 Autotymp (Madison, WI) or equivalent tympanometer will be recorded when the TM appears healed otoscopically.

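### Section 17.6 assigns secondary categorical data to a paired form of Fisher's exact test, which does not fit independent arms and would be uninformative if applied to the salvage rate

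*Combined protocol and SAP*

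**What the plan says.** The whole of section 17.6 is one sentence: "Secondary analysis of categorical data will be performed using Fisher's exact test for paired samples". It names no variable, no pair and no comparison.

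The rest of the plan supplies the context:

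- Section 5.1, Part A: "subjects will be randomized 3:1 to receive FGF-2 or placebo treatment up to 3 treatments". These are parallel, independent arms.
- The Statistical Analysis part of the Synopsis uses Fisher's exact test, with no mention of pairing, for the sample size of the two-arm comparison (45 and 15 subjects, two-sided 0.05).
- The Synopsis lists among the secondary endpoints "Tympanic membrane perforation closure determined by otoscopic exam and photographic documentation" and "Salvage rate of FGF-2 in patients who fail placebo".
- Section 4.2 words the salvage objective as "Observe salvage rate of FGF-2 treatment in subjects who failed placebo treatment".
- Section 5.1, Part B: "Subjects who received placebo in part A and failed three placebo treatments will crossover to receive unblinded FGF-2 for up to 3 treatments".
- Section 13.2 sets a threshold for clinically significant hearing change, "A change of >10 dB across two frequencies" or a speech discrimination criterion, and says that tympanic membrane mobility "will be recorded when the TM appears healed otoscopically".

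**The concern.** Fisher's exact test conditions on the margins of a table built from two independent groups. For paired binary data the usual exact procedure is McNemar's test, which uses only the discordant pairs. The sentence in 17.6 combines the two, so an analyst cannot carry it out without deciding which half to discard. That decision would be made after the data exist.

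For between-arm endpoints the problem is simple: there are no pairs. For the salvage endpoint it is conditional. Closure on placebo followed by closure on FGF-2 in the same ear is a natural pairing in this design, and 17.6 does not exclude it. If it were used, the first member of each pair would be a failure for every subject, because failing placebo is the entry condition for Part B. The null hypothesis would amount to no closures at all. The question of interest is whether FGF-2 closes more ears than further rounds of edge roughening, gelatin sponge and fibrin glue would. Part B is open label with no concurrent control, so it cannot answer that question.

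**Working it through.** The plan gives no figure for 17.6 or for the salvage analysis, so there is nothing to reproduce. The check has two parts.

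**1. Can any secondary categorical endpoint use a paired Fisher test?**

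- *Closure between arms (Synopsis):* different subjects in each arm, so no pairs.
- *Clinically significant hearing change (13.2):* each subject's value is already a within-subject change. Comparing its frequency between arms needs an independent-groups test.
- *Tympanometry:* scheduled only at the Final Visit (13.1) and recorded once the membrane looks healed (13.2), so there is no baseline partner.
- *Pre- and post-treatment audiometry, if categorised:* pairs exist within a subject, but Fisher's test is not the method for them.
- *Salvage:* pairs exist, but one side is fixed by selection.

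**2. What would happen if 17.6 were applied to salvage?**

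Let m be the number of placebo failures treated in Part B and k the number that close. The placebo side is 0 of m.

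- *Exact McNemar:* all k discordant pairs point the same way, so two-sided p = 2 × 0.5^k. k = 5 gives 0.0625 and k = 6 gives 0.031. Six closures are significant whatever m is.
- *Fisher on 0/m against k/m:* for m = 13 and k = 5, p = 2 × C(13,5)/C(26,5) = 2 × 1287/65780 = 0.039. For m from 10 to 19, five closures give p from 0.033 to 0.046.

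Now suppose FGF-2 adds nothing. Let q be the probability that one three-treatment course closes an ear, the same in both phases. Then m ~ Bin(N, 1−q) and, given m, k ~ Bin(m, q), where N is the number of placebo subjects. Unconditionally k ~ Bin(N, q(1−q)), so the McNemar chance is P(k ≥ 6). For N = 15 and q = 0.20, q(1−q) = 0.16 and P(k ≥ 6) = 0.023. The Fisher chance is the sum over all (m, k) with p ≤ 0.05.

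Inputs:

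- N = 15 from the Synopsis split of 45 and 15. N = 19 is used as well, because the Synopsis also plans 75 subjects and 75/4 = 18.75.
- q is assumed. Section 3.2 cites closure in 1 of 10 human controls given sponge and glue, assessed at three weeks. Read as a rate per course, q = 10%. Read as a rate per application over three applications, q = 1 − 0.9³ = 27.1%. Section 3.1 cites animal control rates of 41% and 37%, so 40% serves as the upper end.

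Chance of p ≤ 0.05 for an inert drug, McNemar / Fisher:

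| q | 15 placebo subjects | 19 placebo subjects |
|---|---|---|
| 10% | 0.1% / 0.8% | 0.5% / 2.3% |
| 20% | 2.3% / 7.8% | 7.0% / 17.6% |
| 27.1% | 5.8% / 15.8% | 15.6% / 31.7% |
| 30% | 7.5% / 19.1% | 19.3% / 36.8% |
| 40% | 12.7% / 28.3% | 29.5% / 49.4% |

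**Check on the replacement.** The ordinary two-sided Fisher test for 45 against 15 independent subjects has an exact type I error of 0.021 at a common rate of 10%, 0.035 at 27.1% and 0.033 at 41%, all below 0.05. For a salvage rate reported with an exact 95% interval, 6 of 14 would give 18% to 71% and 12 of 14 would give 57% to 98%.

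**The case against.** The strongest reply is that 17.6 contains only a slip in naming a test. It does not mention salvage. Section 4.2 asks to observe a rate, section 5.1 describes an observation, and no salvage hypothesis, reference rate or p-value appears anywhere. The word paired may have been meant for audiograms before and after treatment. A usable between-arm test is also named elsewhere: ordinary Fisher in the Synopsis, and a Cochran-Mantel-Haenszel option in section 17.5 for efficacy data from the randomised phase.

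Most of this stands. A reader might infer that the plan commits to testing each subject's FGF-2 result against that subject's own placebo failure and to reporting a significant rescue effect. The documents do not say so, and the salvage wording points towards description. A reader might also fix 13 of 15 placebo subjects as failures and then let 20% to 40% of them close in Part B with an inert drug. That gives much larger false-positive chances, up to 43% (McNemar) and 65% (Fisher) at 40%. The two assumptions conflict: 13 failures in 15 implies about 13% closure per course (2/15), whereas 40% closure implies 9 expected failures (15 × 0.6). Linking the two gives the table above, and at 10% both tests stay below 5%.

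The reply does not rescue the sentence itself. Section 17.6 is the only rule devoted to secondary categorical data. It covers all such data without exception, and it conflicts with the sections that name a usable test. The pre/post reading would need a different test as well.

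**Conclusion.** The rule in 17.6 is wrong as written for between-arm categorical secondary endpoints. This rests on the text alone and needs no assumption.

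The salvage part holds only if 17.6 is applied to that endpoint. In that case a paired test could move only towards FGF-2, and a significant result could not be attributed to the drug at any closure rate. The numerical risk depends on assumed rates. With 15 placebo subjects it passes 5% between 10% and 20% closure per course for Fisher, and between 20% and 27.1% for McNemar. With 19, both pass 5% between 10% and 20%. The model gives every ear the same closure probability in both phases, so the risk is lower if placebo failures are harder ears to close.

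Only secondary analyses are affected. Neither the primary comparison nor the sample size changes.

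**What to change.** Replace the sentence in 17.6 with:

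> Categorical secondary endpoints in the Randomized Treatment phase are compared between arms with Fisher's exact test for two independent groups. The Part B salvage rate is reported descriptively as the number closed over placebo failures who received open-label FGF-2, with an exact 95% confidence interval and no hypothesis test against the subject's own placebo result, and is interpreted as uncontrolled.

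Two points need reconciling at the same time. Section 13.5 requires at least one treatment and a 21-day follow-up visit before a subject is evaluable for efficacy, whereas the Synopsis counts a subject who discontinues as not improved. The salvage denominator should state which rule governs a crossed-over subject who is treated but has no follow-up visit. If pre/post audiometric categories were the data intended as paired, 17.6 should name them and give a paired method separately.

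The cost is a change of wording. The sponsor gives up only a salvage p-value that would not have been valid.

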No apparent risks of ototoxicity were observed in Kase et al's 2007 study of two groups of 21 healthy guinea pigs, in which 100µg of b-FGF was applied four times to the left external auditory canal and middle ear using a gelatin sponge container (Spongel; Astellas Pharma Inc, Tokyo, Japan) for Group A (n=10) or myringotomy and then a gelatin sponge insertion into the middle ear for Group B (n=11). The right ears served as the controls. The cochleae were examined one week post application in addition to measuring endocochlear DC potential (EP). Topical application of the drug did not cause significant reduction in EP or any degenerative changes in the cochlea.

A more recent study conducted by Hakuba et al (2014) demonstrated that a sustained b-FGF formulation could be applied to and successfully close eardrum perforations in guinea pigs using a gelatin hydrogel. In this equivalent 3-group model of 24 guinea pigs (b-FGF-gelatin hydrogel group, saline gelatin hydrogel group, and control group), total tympanic membrane perforations were formed using a CO₂ laser. All 8 (100%) TMPs in the b-FGF gelatin hydrogel group achieved closure of the perforation, compared to 3 out of the 8 ears in the saline-gelatin group (37%) and none of the control group (0%). In addition to improving closure rates, the application of b-FGF also induced improved regeneration of the fibrous layer in addition to the mucosal and epithelial layers. Overall, this study showed promising results in terms of *in vitro* and *in vivo* benefits. *In vitro*, there was fibroblast growth as well as migration and growth, via FGF receptors, of various cells involved in wound healing (including vascular endothelial cells, vascular smooth muscle cells, and epithelial cells). Application of b-FGF also promoted neovascularization and granulation tissue formation.

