13.1 Schedule of Assessments

Visit	0	1	2	3	4	5	6	7	Final Visit
Screening	Day 1 (± 7 days)	Day 22 (± 7 days)	Day 43 (± 7 days) As Needed	Day 64 ⁵ (± 7 days) As Needed	Day 85 ⁶ (± 7 days) As Needed	Day 106 ⁶ (± 7 days) As Needed	Day 127 ⁶ (± 7 days) As Needed		F/U ⁷ (± 7 days) As Needed
Informed Consent	X								
Inclusion/Exclusion Criteria	X								
Medical History Related to the Tympanic Membrane	X								
Otologic Exam	X								X
Vital Signs	X ²	X ²	X	X	X	X	X	X	X
Laboratory Evaluation /CBC, Basic Metabolic Panel, HbA1C/	X								X
Pregnancy Test ³	X								
Prior/Concomitant Medication	X	X	X	X	X	X	X	X	X
TM photography	X ^{1,2}	X ^{1,2}	X ¹	X ¹	X ¹	X ¹	X ¹	X ¹	X
Audiology		X ^{1,2}	X ¹	X ¹	X ¹	X ¹	X ¹	X ¹	X
Tympanometry									X
Study Drug Administration	X	X ⁴	X ⁴	X ⁴	X ⁴	X ⁴	X ⁴		
Review of Adverse Events	X	X	X	X	X	X	X	X	X

¹To be completed prior to administration of the investigational drug.

²This may be performed during the screening visit or during Day 1 Visit. Note: The first audiogram may have been performed within 60 days prior to subjects' enrollment.

³Women of child bearing potential will be required to have a negative pregnancy test. Either serum or urine tests are acceptable. Until study completion, adequate form of contraception must be ensured.

⁴Treatment given if the perforation has not closed at this visit.

⁵If the perforation has not closed at this visit, then the subject will be assigned to the other treatment group. The subject will then follow the same schedule of procedures as stated for Visit 5, Visit 6, Visit 7, and Final Visit.

⁶These visits will be completed by subjects that have been assigned to the other treatment arm and whose perforation still has not closed.

⁷The final study visit occurs 2 months (+/- 7 days) after the subject's last follow-up visit. The subject's last follow-up visit occurs when the subject's perforation is determined to be closed, or when the subject has completed the maximum number of study visits without perforation closure

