13.3 Safety Measurements

- Adverse events by severity and causality as described in section 7.7
- Laboratory evaluations including SMA-21 and CBC with differentials.
- Clinically meaningful changes in vital signs including temperature, blood pressure, weight, pulse, and respiratory rate

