17.2 Subject Populations

The following populations will be used for the analysis of data for this study:

Per Protocol (PP) Population: All subjects who have been selected and received the specified drug at Visit 1 and do not have any important protocol deviations will be included in the PP population. The PP population will be the primary population for the analysis of efficacy.

Safety Population: All subjects who received the drug will be included in the safety population. The safety population will be the primary population for analysis of demographic, accountability, and safety measures.

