17.5 Efficacy Analysis

Efficacy data from the Randomized Treatment phase will be evaluated by inspection, using student T-test, Cochran Mantel Hansel, or Kruskal-Wallis tests as appropriate; without conservation of alpha at 0.05. An interim analysis will be completed after approximately 50% of the study subjects (n=30) have been accrued.

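### Hearing is tested at Visits 1–7 and the Final Visit and its loss is a reason to stop treatment, yet no audiometric safety analysis is planned, so a measured loss reaches the safety tables only if recorded as an adverse event

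*Combined protocol and SAP*

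**What the plan says.** **Hearing as a harm.** Section 3.1 raises ototoxicity as a nonclinical question and reports of a guinea pig study that "No apparent risks of ototoxicity were observed". The Synopsis lists "clinically significant sensorineural hearing loss" among the ear complications that rule out further treatment. Section 7.3 has a similar list, which names hearing loss without the sensorineural qualifier.

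**Data collected.** Section 13.1 and Sections 14.2 to 14.8 schedule an audiogram at Visits 1 to 7 and at the Final Visit. The baseline test may come from screening or earlier: "The first audiogram may have been performed within 60 days prior to" enrollment.

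**Where hearing is placed.** Section 13.2 (Efficacy Measurements) holds the audiometric tests and the per-subject criterion: "A change of >10 dB across two frequencies or a change in speech discrimination of $> 20\%$ will be considered clinically significant". It gives no direction of change.

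**Safety.** Section 13.3 lists adverse events, laboratory evaluations and "Clinically meaningful changes in vital signs including temperature, blood pressure, weight, pulse, and respiratory rate". Section 18 says "Safety will be assessed by evaluation of adverse events and clinical laboratory results". Section 21 gives laboratory results shifts from baseline. None of these names audiometry.

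**Efficacy.** Section 17.5 says "Efficacy data from the Randomized Treatment phase will be evaluated by inspection". Section 17.2 says "The PP population will be the primary population for the analysis of efficacy". Section 4.2 has a secondary objective of measuring hearing change in all study subjects. Section 17.6 covers secondary categorical data in one sentence and names no variable, visit or population.

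**The concern.** The protocol treats hearing loss as serious enough to end treatment and measures hearing repeatedly, but the safety plan does not use those measurements. Laboratory tests, scheduled only at screening and the Final Visit, get a shift analysis. Audiograms, scheduled at eight visits, do not.

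The planned efficacy analysis is a poor substitute. Closing a perforation is expected to improve hearing, so a comparison of mean change can show a gain while a few ears lose hearing. The one stated efficacy period is the randomized phase, so no audiometric analysis is specified for Part B, where most placebo subjects may receive FGF-2.

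At stake is whether the trial can give a rate of measured hearing loss after FGF-2, with a confidence interval, over everyone exposed. As written, the safety conclusion rests on which losses were recorded as events.

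**Working it through.** The point concerns which data are analysed, in whom and over what period. The plan states no figure to reproduce, so the check is first a comparison of sections and then arithmetic for scale.

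**1. Sections side by side**

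| Item | Scheduled | Safety measure (13.3) | Safety analysis (18, 20, 21) |
|---|---|---|---|
| Adverse events | Every visit | Yes | Yes, by treatment group |
| Laboratory tests | Screening, Final Visit | Yes | Yes, shifts from baseline |
| Vital signs | Every visit | Yes | Not named |
| Audiometry | Visits 1–7, Final Visit (8 of 9 columns) | No | No |

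**2. Routes by which a measured loss could be analysed**

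- *Adverse events.* Section 15.1 counts any unfavorable change in function as an adverse event, and Section 20 reports all treatment-emergent events with no limit by phase or to the Per Protocol set. This route is open. However, events are gathered by spontaneous report and open-ended questions, and no section says that a shift beyond the 13.2 threshold must be recorded. Section 20 tabulates by treatment group and gives no rule for crossed-over subjects.
- *Efficacy.* Section 17.5 covers Part A. Section 17.6 sets no phase limit but does not name hearing.
- *Safety-population audiometry.* None is planned.

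**3. Size of Part B**

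Inputs: 45 FGF-2 and 15 placebo subjects (Synopsis, Statistical Analysis). Placebo closure is assumed to be 10%, the control rate in the gelatin sponge and fibrin glue study cited in Section 3.2.

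- Expected crossovers: 15 × (1 − 0.10) = 13.5, so about 13.
- Share of FGF-2 ears: 13 / (45 + 13) = 22%.
- If placebo closure were 41% (the control rate in the chinchilla study in Section 3.1): 15 × 0.59 = 8.9, so about 9.
- If 75 are enrolled 3:1 (about 56 and 19) with 10% closure: 19 × 0.90 = 17.1, so about 17.

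**4. Upper bound on the loss rate with no losses seen**

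One-sided 95% bound = 1 − 0.05^(1/n).

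| FGF-2 ears | n | Bound |
|---|---|---|
| Part A only | 45 | 6.4% |
| Part A + 9 crossovers | 54 | 5.4% |
| Part A + 13 crossovers | 58 | 5.0% |
| 75 enrolled, Part A only | 56 | 5.2% |
| 75 enrolled, Part A + 17 crossovers | 73 | 4.0% |

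**5. How a mean can hide losses (illustration only)**

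Take 92% closure and a 13.6 dB gain in closers, both from the atelocollagen patch study in Section 3.2, and assume no change in non-closers.

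- FGF-2 mean gain: 0.92 × 13.6 = 12.5 dB.
- Suppose 3 of the 45 ears, otherwise closers, lose 20 dB (assumed): 0.92 × 45 = 41.4 closers, and ((41.4 − 3) × 13.6 − 60) / 45 = 10.3 dB.
- Placebo at 10% closure: 0.10 × 13.6 = 1.4 dB.

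The mean still favours FGF-2 clearly with three large losses in the arm.

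**The case against.** The best defence is that hearing loss is already covered. A change in function is an adverse event by definition. The wording that leaves recording to the investigator's judgement in Section 15.1 applies to laboratory abnormalities, not to loss of function. Adverse events are assessed at the same Part B and Final Visits as the audiograms, and the tables include events that cause withdrawal. This stands. A reader might infer that losses in Part B, at the Final Visit or in excluded subjects are never tabulated; the documents do not support that.

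Nor do they support the inference that hearing is analysed only in Part A and only in the Per Protocol set. That set is called primary, not sole; Section 4.2 speaks of all study subjects; Section 17.6 has no phase limit. Stopping for hearing loss is not stated to be a protocol deviation, so it need not remove a subject from the Per Protocol set. That Final Visit audiograms go unanalysed is an inference from one phrase in Section 17.5.

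The mean-change illustration is also open to attack. The closure and gain figures come from a different product and dose, the placebo figure comes from another study, and the three ears losing 20 dB are assumed. In addition, Section 13.2 has a per-subject criterion that could be analysed as categorical data, so a mean is not clearly the only hearing analysis. The illustration shows a mechanism, not an expected result.

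What the defence does not supply is a link between the audiogram and the adverse event form, or any planned table of audiometric worsening in the safety population.

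**Conclusion.** The point holds in this form: hearing is measured at eight scheduled visits and its loss is a reason to stop treatment, but no audiometric safety analysis is planned in the safety population across Part A, Part B and the Final Visit. A measured loss enters the safety tables only if it is recorded as an adverse event, and the 13.2 threshold does not trigger recording.

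The size is modest but real. Under 10% placebo closure, about 22% of FGF-2 ears would be crossover ears with no specified hearing analysis. Including them moves the zero-event upper bound from 6.4% to about 5.0% (5.4% if placebo closure were 41%). These bounds depend only on the number of ears and say nothing about whether losses will occur.

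It would go too far to say that the trial cannot report any rate of hearing loss, since adverse event incidence will be tabulated. What it lacks is a planned rate based on the measurements.

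Separately, the two discontinuation statements differ. The Synopsis refers to sensorineural loss after a first treatment that has not closed the perforation; Section 7.3 refers to hearing loss after three treatments. They must be reconciled.

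**What to change.** 1. Add pure-tone thresholds and speech discrimination to Section 13.3 and to the first sentence of Section 18.
2. Add one safety-population table (all treated subjects, placebo included) giving the number and percentage of treated ears, with exact confidence intervals, that worsen from the pre-treatment audiogram by the Section 13.2 threshold, in the direction of loss.
3. For the randomized comparison, use one audiogram per subject, so that the count does not depend on the number of visits: Visit 2, which is scheduled for everyone, and the last Part A audiogram.
4. Report Part B FGF-2 separately, with the Visit 4 audiogram before crossover as its baseline.
5. Report the Final Visit descriptively by treatment actually received. A crossed-over subject's Final Visit follows FGF-2 and must not be counted as placebo.
6. Label any worst-visit count as descriptive. Non-closers have more audiograms than early closers and so more chances to show a loss; if FGF-2 closes more ears, such a count would favour it.
7. Keep mean change as the efficacy analysis.
8. Reconcile the hearing-related discontinuation wording in the Synopsis and Section 7.3.

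The cost is a few lines of text and one extra table. Every audiogram is already scheduled, so no new tests are needed.
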